4.3.6. Immunogenicity Analyses

For the immunogenicity assessment, a binding antibody assay will be performed for anti-drug antibody (ADA).

The binding ADA results at each available timepoint, including Predose as well as at any time post-baseline, will be summarised. Summary statistics for the titre result will also be presented by visit.

The binding ADA results at each visit will be categorised as negative, transient positive (defined as a single confirmatory positive immunogenic response that does not occur at the final study assessment) or persistent positive (defined as a confirmatory positive immunogenic response for at least 2 consecutive assessments or a single result at the final study assessment). In addition, the highest post-baseline binding ADA confirmatory result obtained for a subject will be summarised. Subjects with both positive and negative results will be identified in the positive category. Summary statistics for highest titre result will also be presented.

A summary of adverse events by highest post-baseline binding ADA result will be produced.

A summary of positive confirmation binding ADA assay results in the subset of subjects who did not have a positive confirmation binding ADA result prior to the dosing of study treatment will also be presented.

4.4. Exploratory Endpoints Analyses

No exploratory endpoints analyses are planned as of now.

4.5. Safety Analyses

Please refer to section [4.3](#).

4.5.1. Extent of Exposure

This is an open-label, single dose study with two dose cohorts. Exposure data will be listed for the participants who received treatment.

4.6. Other Analyses

Population PK analyses may be conducted under the direction of CPMS. These analyses will be described in a separate document.

4.7. Interim Analyses

No interim analysis is planned in this study.

4.8. Changes to Protocol Defined Analyses

There were no changes or deviations to the originally planned statistical analysis specified in the protocol (Dated: 27-April-2021).

5. SAMPLE SIZE DETERMINATION

There are no formal calculations of power or sample size for this study. The sample size of approximately 10 participants per cohort will be enrolled into the study to obtain at least 6 participants per cohort with at least 18-week PK data has been chosen based on feasibility.

Any impact of missing data and/or dropout will be assessed during the study. Specifically, in each cohort, if there are less than 6 participants with at least 18-week PK data, a maximum of up to 6 additional participants will be recruited in order to target at least 6 participants with at least 18-week PK data. In the case when there are less than 6 participants with at least 18-week PK data available in each cohort after the recruitment of additional participants, population PK analysis will be used to overcome the potential impact of missing data and/or dropout.

For each cohort, with 6 participants with at least 18-week PK data, assuming that the coefficients of variation% (CV%) of C_{max} and AUC(0-∞) is 25.4% and 28.5% respectively (from global FTIH study, GSK Document Number [2019N411063 00](#)), it is estimated that the lower and upper bounds of the 95% confidence interval (CI) would lie within 30.0% of the point estimate for C_{max} and 34.1% of the point estimate for AUC(0-∞).

5.1. Sample Size Sensitivity

Different participant numbers with at least 18-week PK data and the corresponding precisions of C_{max} and AUC(0-∞) are provided in the table 2 below. It assumes the CV% of C_{max} and AUC(0-∞) is 25.4% and 28.5% respectively.

Table 1 Different Participant Numbers and Corresponding Precisions

Pharmacokinetic parameter	PPD	Precision (Half width of 95% confidence interval)
Cmax		30.0%
		26.0%
		23.2%
		21.2%
		19.6%
AUC (0-∞)		34.1%
		29.5%
		26.3%
		24.0%
	22.1%	

6. SUPPORTING DOCUMENTATION

6.1. Appendix 1 Study Population Analyses

Unless otherwise specified, the study population analyses will be based on the Safety Analysis Set. A summary of the number of participants in each of the participant level analysis set will be provided based on Screened Analysis Set.

Study population analyses including analyses of participant disposition, demographic and baseline characteristics, protocol deviations, and prior and concomitant medications. Details of the planned displays are presented in OPS document.

6.1.1. Participant Disposition

A summary of the number and percentage of participants who completed the study as well as those who prematurely withdrew from the study will be provided. Reasons for study withdrawal and outcome of adverse events which led to study withdrawal will be summarized. Additionally, screening status and reasons for screen failure will be summarised.

Listings of reasons for screen failure and reasons for study withdrawal will be generated.

6.1.2. Demographic and Baseline Characteristics

The demographic characteristics including age, gender, ethnicity, height, weight, body mass index (BMI) at screening and race will be summarized with descriptive statistics. In addition, the following age categories will be summarized: 18-64 based on the Safety Analysis Set. Body Mass Index (BMI) is calculated as $\text{weight (kg)} / [\text{height (m)}]^2$, will be presented as for summary statistics with 1 decimal place.

A summary of family history of cardiovascular risk factors will be provided.

Past medical conditions and current medical conditions as of screening will be summarized respectively.

6.1.3. Protocol Deviations

Important protocol deviations will be summarized and listed.

Protocol deviations will be tracked by the study team throughout the conduct of the study. These protocol deviations will be reviewed to identify those considered as important as follows:

- Data will be reviewed prior to freezing the database to ensure all important deviations are captured and categorised in the protocol deviations dataset.
- This dataset will be the basis for the summaries of important protocol deviations.

No per-protocol analysis is planned for this study.

6.1.4. Prior and Concomitant Medications

Prior and concomitant medication tables will report by Anatomical Therapeutic Chemical (ATC) level 1 and ingredient. Multi-ingredient medications will be presented according to their combination ATC classification rather than the classification of the ingredients.

Summaries will be provided for the medications by prior medications, pre-treatment concomitant medications, and on-treatment concomitant medications.

Study phase for concomitant medication

Study Phase	Definition
Prior	If concomitant medication end date is not missing and is before 28 days prior to screening visit
Concomitant	Any medication that is not considered as prior. These will be further split into those that were started prior to dosing and those started after dosing as follows: 
 Pre-Treatment: Start Date and Time < Dosing Date and Time On-Treatment: Start Date and Time >= Dosing Date and Time

6.1.5. Study Intervention Compliance

Not applicable.

6.1.6. Additional Analyses Due to the COVID-19 Pandemic

No additional analyses due to the COVID-19 pandemic are planned as of now.

6.2. Appendix 2 Data Derivations Rule

6.2.1. Criteria for Potential Clinical Importance

Reference ranges for all laboratory parameters collected throughout the study are provided by the laboratory. A laboratory value that is outside the reference range is considered either high abnormal (value above the upper limit of the reference range) or low abnormal (value below the lower limit of the reference range). Note: a high abnormal or low abnormal laboratory value is not necessarily of clinical concern.

In addition, the following criteria will be used to flag potential clinical importance:

6.2.1.1. Laboratory Values

Haematology			
Parameter	Units	Category	Clinical Concern Range

			Low Flag (< x)	High Flag (> x)
Hematocrit	Ratio of 1	Male		0.54
		Female		0.54
		Δ from BL	↓0.075	
Hemoglobin	g/L	Male		180
		Female		180
		Δ from BL	↓25	
Lymphocytes	x10 ⁹ /L		0.8	
Neutrophil Count	x10 ⁹ /L		1.5	
Platelet Count	x10 ⁹ /L		130	550
While Blood Cell Count (WBC)	x10 ⁹ /L		3	15
%Reticulocyte	%		0.5	1.5

Clinical Chemistry				
Parameter	Units	Category	Clinical Concern Range	
			Low Flag (< x)	High Flag (> x)
Albumin	g/L		30	
Calcium	mmol/L		2	2.75
Creatinine	umol/L	Δ from BL		↑ 44.2
Glucose	mmol/L		3	9
Potassium	mmol/L		3	5.5
Sodium	mmol/L		130	150

Liver Function			
Parameter	Units	Category	Clinical Concern Range
ALT/SGPT	U/L	High	$\geq 2x$ ULN
AST/SGOT	U/L	High	$\geq 2x$ ULN
AlkPhos	U/L	High	$\geq 2x$ ULN
T Bilirubin	$\mu\text{mol/L}$	High	$\geq 1.5x$ ULN
T. Bilirubin + ALT	$\mu\text{mol/L}$	High	1.5xULN T. Bilirubin +
	U/L		$\geq 2x$ ULN ALT

6.2.1.2. ECG

Parameter	Units	Clinical Concern Range	
		Lower	Upper
Absolute			
Absolute QTcF Interval	msec		> 450 ¹
Absolute PR Interval	msec	< 110 ¹	> 220 ¹
Absolute QRS Interval	msec	< 75 ¹	> 110 ¹
Absolute QT	msec		> 600
Change from Baseline			
Increase from Baseline QTcF	msec		> 60 ¹

NOTES: ¹ Represent standard ECG Values of PCI for HV studies.

6.2.1.3. Vital Signs

Parameter	Units	Clinical Concern Range
-----------	-------	------------------------

		Lower	Upper
Systolic Blood Pressure	mmHg	< 85	> 160
Diastolic Blood Pressure	mmHg	< 45	> 100
Heart Rate	bpm	< 40	> 110

6.2.2. Study Phases and Treatment States

Assessments and events will be classified according to the time of occurrence relative to dosing.

6.2.2.1. Treatment States for Safety and Pharmacodynamic Data

Treatment State	Definition
Pre-Treatment	Date and Time \leq Dosing Date and Time
On-Treatment	Date and Time > Dosing Date and Time

6.2.2.2. Study Phases for Concomitant Medication

Study Phase	Definition
Prior	If the medication end date is not missing and is before 28 days prior to screening visit
Concomitant	Any medication that is not considered as prior. These will be further split into those that were started prior to dosing and those started after dosing as follows: 
 Pre-Treatment: Start Date < Dosing Date On-Treatment: Start Date \geq Dosing Date

NOTES: Please refer to [section 6.2.6: Handling of Missing and Partial Dates](#) for concomitant medication. Use the rules in this table if concomitant medication date is completely missing.

6.2.2.3. Study Phases for Adverse Events

Study Phase	Definition
Pre-Treatment	AE Start Date and time < Study Treatment Start Date and time
On-Treatment	If AE Start date and time \geq Study treatment start date and time

Onset Time Since Dose (Days)	If Dose Date > AE Start Date = AE Start Date - Treatment Start Date If Dose Date ≤ AE Start Date = AE Start Date - Treatment Start Date + 1 Missing otherwise.
Duration (Days)	AE End Date - AE Start Date + 1
Drug-related	If relationship is marked 'YES' on Inform/CRF OR value is missing.

6.2.2.4. Treatment Emergent Flags for Adverse Events

Flag	Definition
Treatment Emergent	
 If AE start date is on or after treatment start date

NOTES: Time of study treatment dosing and start/stop time of AEs should be considered.

6.2.3. Study Day and Reference Dates

The safety reference date is the study intervention start date and will be used to calculate study day for safety measures.

The study day is calculated as below:

- Assessment Date = Missing → Study Day = Missing
- Assessment Date < Reference Date → Study Day = Assessment Date – Ref Date
- Assessment Date ≥ Reference Date → Study Day = Assessment Date – Ref Date + 1

6.2.4. Assessment Window

- Scheduled and unscheduled assessments will be considered for summary tables that display data by visit.
- All scheduled and unscheduled data will be considered for each assessment window.
- In summary tables, only scheduled timepoints for that cohort and assessment will be displayed. For example, complement data are not expected to be collected at all timepoints; if any complement data were taken e.g. at Week 2 then they will not be summarised.
- Only 1 value per participant, assessment and assessment window will be used in the calculation of summary statistics for that assessment; if a participant has more than 1 valid observation within an assessment window then the observation closest to the planned time will be used. If 2 observations are equidistant from the planned timepoint then the mean of the values will be taken.
-

Analysis Set / Domain	Parameter (if applicable)	Target	Analysis Window		Analysis Timepoint
			Beginning Timepoint	Ending Timepoint	
Safety and Complement (C3 & C4) data presented by visit.	ECG, vital signs, laboratory (clinical chemistry, urinalysis and haematology), complement (C3 & C4)	Day -1	Any time on Day -1. Note that if there is no scheduled Predose-assessment for the parameter then latest valid result prior to Day 1 dosing should be used		Day -1
	Immunogenicity, ECG, vital signs	Day 1 (Predose)	≤ 2h prior to dosing time		Day 1 (Predose)
	ECG, vital signs	Day 1 (2h)	Day 1 (1.25h)	Day 1 (2.75h)	Day 1 (2h)
	ECG, vital signs	Day 1 (8h)	Day 1 (7.25h)	Day 1 (8.75h)	Day 1 (8h)
	ECG, vital signs, haematology	Day 2 (24h)	Day 2 (23h)	Day 2 (25h)	Day 2 (24h)
	ECG, vital signs, haematology	Day 3 (48h)	Day 3 (47h)	Day 3 (49h)	Day 3 (48h)
	ECG, vital signs, haematology	Day 5	Assessment must have been done on Day 5		Day 5
	ECG, vital signs, laboratory (clinical chemistry, urinalysis and haematology), complement (C3 & C4)	Day 8 (Week 1)	± 1 day		Day 8 (Week 1)
	ECG, vital signs, haematology	Day 15 (Week 2)	± 1 day		Day 15 (Week 2)
	Immunogenicity, ECG, vital signs, laboratory (clinical chemistry, urinalysis and haematology), complement (C3 & C4)	Day 29 (Week 4)	± 3 day		Day 29 (Week 4)
	ECG, vital signs, laboratory (clinical chemistry, urinalysis and haematology), complement (C3 & C4)	Day 57 (Week 8)	± 3 day		Day 57 (Week 8)
	Immunogenicity, ECG, vital signs, laboratory (clinical chemistry, urinalysis and haematology), complement (C3 & C4)	Day 85 (Week 12)	± 3 day		Day 85 (Week 12)

Analysis Set / Domain	Parameter (if applicable)	Target	Analysis Window		Analysis Timepoint
			Beginning Timepoint	Ending Timepoint	
	ECG, vital signs, heamatology	Day 127 (Week 18)	± 3 day		Day 127 (Week 18)
	ECG, vital signs, laboratory (clinical chemistry, urinalysis and heamatology), complement (C3 & C4)	Day 169 (Week 24)	± 3 day		Day 169 (Week 24)
	Immunogenicity, ECG, vital signs, laboratory (clinical chemistry, urinalysis and heamatology), complement (C3 & C4)	Day 183 (Week 26)	± 3 day		Day 183 (Week 26)

6.2.5. Multiple measurements at One Analysis Time Point

Mean of the measurements (e.g., ECG) will be calculated and used in any derivation of summary statistics but if listed, all data will be presented.

If there are two values within a time window the value closest to the target day for that window will be used. If values are the same distance from the target, then the mean will be taken.

Participants having both High and Low values for Normal Ranges at any post-baseline visit (including post-baseline unscheduled assessments) for safety parameters will be counted in both the High and Low categories of “Any visit post-baseline” row of related summary tables. This will also be applicable to relevant Potential Clinical Importance summary tables.

6.2.6. Handling of Missing and Partial Dates

Element	Reporting Detail
General	
 Partial dates will be displayed as captured in participant listing displays.
Adverse Events	
 The eCRF allows for the possibility of partial dates (i.e., only month and year) to be recorded for AE start and end dates; that is, the day of the month may be missing. In such a case, the following conventions will be applied for calculating the time to onset and the duration of the event: 
 Missing Start Day or Start Time: First day of the month or start of the day will be used, respectively, unless this is before the start date or time of study treatment; in this case the study treatment start date and time will be used and hence the event is considered On-treatment as per section 6.2.2: Study Phases and Treatment States.

Element	Reporting Detail
	
 Completely missing start or end dates will remain missing, with no imputation applied. Consequently, time to onset and duration of such events will be missing.
Concomitant Medications/ Medical History	
 Partial dates for any concomitant medications recorded in the CRF will be imputed using the following convention: 
 If the partial date is start date, a '01' will be used for the day and 'Jan' will be used for the month. If the partial date is a stop date, a '28/29/30/31' will be used for the day (dependent on the month and year) and 'Dec' will be used for the month. The recorded partial date will be displayed in listings.
Age	
 Only year of birth is collected on eCRF. Day and Month of birth are imputed as 30 June. Age is derived using the date of the screening visit. All participants with imputed age of 17 or 18 years will be source data verified, and presence/ absence of protocol deviation on the inclusion criteria #1 will be taken into consideration in the derivation for the analysis variable age. Birth date will be presented in listings as 'YYYY'.

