### **8.3.1. Time Period and Frequency for Collecting AE and SAE Information**

- All AEs/SAEs will be collected from the start of intervention until the last visit at the time points specified in the SoA (Section 1.3.). However, any SAEs assessed as related to study participation (e.g., study intervention, protocol-mandated procedures, invasive tests, or change in existing therapy) or related to a GSK product will be recorded from the time a participant consents to participate in the study.
- Medical occurrences that begin before the start of study intervention but after obtaining informed consent will be recorded as Medical History/Current Medical Conditions not as AEs.
- All SAEs will be recorded and reported to the sponsor or designee immediately and under no circumstance should this exceed 24 hours, as indicated in Appendix 3. The investigator will submit any updated SAE data to the sponsor within 24 hours of it being available.
- Investigators are not obligated to actively seek information on AEs or SAEs after the conclusion of the study participation. However, if the investigator learns of any SAE, including a death, at any time after a participant has been discharged from the study, and he/she considers the event to be reasonably related to the study intervention or study participation, the investigator must promptly notify the sponsor.

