4.3.1.2. Adverse Event Analyses

Adverse events analyses including the analysis of AEs, SAEs, and other significant AEs will be based on GSK Core Data Standards. AEs will be coded using the standard MedDRA and grouped by system organ class.

A table will be provided with a high-level summary of the subject incidence of any AEs, on-treatment AEs, drug-related AEs, AEs leading to study withdrawal, any SAEs, on-treatment SAEs, drug-related SAEs, fatal SAEs and drug-related fatal SAEs.

Subject incidence of all on-treatment AEs, drug-related AEs, and AEs leading to study withdrawal will be tabulated by system organ class and preferred term in descending order of frequency.

Summaries of on-treatment AEs by system organ class, preferred term and maximum intensity.

Subject incidence and occurrence of common ($\geq 5\%$) non-serious on-treatment AEs and serious on-treatment AE will be tabulated by system organ class and preferred term in descending order of frequency.

Summaries of non-serious drug-related AEs by preferred term in any dose cohort will be provided in descending order of frequency.

All AEs will be listed.

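### The SAP's rule for a missing AE start day or time moves an event to the dosing time even when its recorded month, day or stop date already places the onset before dosing

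*SAP*

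**What the plan says.** SAP 6.2.6 introduces its adverse event rule by noting that "The eCRF allows for the possibility of partial dates (i.e., only month and year) to be recorded for AE start and end dates". It then states that "the following conventions will be applied for calculating the time to onset and the duration of the event". The rule itself is labelled as covering a missing start day or a missing start time. The default is the first of the month when the day is missing, or midnight of the recorded day when the time is missing, "unless this is before the start date or time of study treatment; in this case the study treatment start date and time will be used". The rule adds that an event moved in this way counts as On-Treatment. A start date that is missing altogether is not imputed.

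SAP 6.2.2.3 defines the Pre-Treatment phase as "AE Start Date and time < Study Treatment Start Date and time"; a start at or after dosing is On-Treatment. The same table gives the onset and duration formulas and sets the drug-related flag from a separate item, the recorded relationship (yes or missing).

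Protocol 8.3.1 collects AEs from the start of intervention and sends earlier occurrences to medical history. The exception is SAEs attributed to study participation or "related to a GSK product will be recorded from the time a participant consents to participate in the study".

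SAP 4.3.1.2 reports subject incidence in separate rows that include "any SAEs, on-treatment SAEs, drug-related SAEs". It also tabulates on-treatment AEs by system organ class and preferred term.

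**The concern.** Moving an uncertain onset to the dosing time is sensible when the event could have begun after dosing: it stops imputation from hiding a post-dose event. SAP 6.2.6 applies the same move when the data leave no such doubt. Three patterns are affected:

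- the day is missing, but the recorded month is earlier than the dosing month;
- the day is missing, but the stop date is before dosing;
- the calendar day is recorded and is before dosing, and only the clock time is missing.

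In each, the imputed start is before dosing, the rule replaces it with the dosing time, and the event leaves the phase that SAP 6.2.2.3 would give it. At stake is whether the on-treatment SAE row and the on-treatment tables contain an event that began before any drug was given. Time to onset and duration would also be wrong. AE and SAE incidence is a secondary endpoint in two small cohorts without a control group, so one misplaced event would show.

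**Working it through.** The plan states no figure to reproduce here. The check applies its rules literally to test events.

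**Inputs.** Start rule: SAP 6.2.6. Phase, onset and duration: SAP 6.2.2.3. Dosing on 10 June at 09:00 is an assumption for illustration only.

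**Formulas.**
- Onset = start date − dose date if the start date is before the dose date; otherwise start date − dose date + 1.
- Duration = end date − start date + 1.

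**Control.** Start 5 June 08:00, end 7 June. Nothing is missing, so nothing is imputed: Pre-Treatment, onset 5 − 10 = −5, duration 7 − 5 + 1 = 3 days.

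**Onset settled as pre-dose by the recorded data, rule as written.** Every start below becomes 10 June 09:00, On-Treatment, onset 10 − 10 + 1 = Day 1.

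| Recorded start | Recorded end | Duration as written | With the condition proposed under the fix |
|---|---|---|---|
| May, day missing | 30 May | −11 + 1 = −10 | Pre-Treatment, onset −40, duration 30 |
| June, day missing | 7 June | 7 − 10 + 1 = −2 | Pre-Treatment, onset −9, duration 7 |
| 5 June, time missing | 7 June | 7 − 10 + 1 = −2 | Pre-Treatment, onset −5, duration 3 |
| 9 June, time missing | 9 June | 9 − 10 + 1 = 0 | Pre-Treatment, onset −1, duration 1 |
| 28 May, time missing | 29 May | −12 + 1 = −11 | Pre-Treatment, onset −13, duration 2 |
| 5 June, time missing | 15 June | 15 − 10 + 1 = 6 | Pre-Treatment, onset −5, duration 11 |

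The third row and the control are the same event; losing the clock time alone changes the phase. In general, an event that ended k calendar days before the dosing day gets duration 1 − k: zero for k = 1 and negative for k of 2 or more.

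**Onset left open by the recorded data.** Dosing-day start, time missing, end 11 June: On-Treatment, Day 1, duration 2. June with day missing, end 15 June: On-Treatment, Day 1, duration 6. Both results are the same with and without the condition, so the conservative handling is kept.

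**Effect on incidence.** One affected participant in a cohort of 10 adds 1/10 = 10 percentage points, or 1/20 = 5 points overall. If a cohort is extended by the permitted 6 participants, the figure is 1/16 = 6.25 points in that cohort.

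**Limit of the check.** In the first row the phase becomes correct, but onset and duration still rest on first-of-month imputation: 1 May lies outside the 14-day screening window.

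**The case against.** Four points on the other side carry weight.

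**Few events can qualify.** Four things must coincide: an SAE between consent and dosing, attribution to study participation or a GSK product, dosing afterwards (the Safety set requires it), and a missing start day or time. Eligibility is reviewed at screening, Day −1 and pre-dose in healthy participants, so someone with such an SAE might well become a screen failure. The documents do not bar dosing after a resolved SAE, so the case is possible but unlikely.

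**The time-only case is arguable.** The lead-in describes partial dates as month and year only. On that reading a fully dated event lacking a clock time falls outside the rule. But the rule itself names a missing start time and supplies a start-of-day default, which would then have no purpose. The missing-day cases do not depend on this reading.

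**The error is visible.** All AEs are listed with partial dates as captured, and a negative duration would stand out among about 20 participants. The rule over-counts on-treatment events and hides none. That limits the harm but does not correct the tables.

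**Stronger readings go too far.** A reader might infer that any AE with an incomplete start is misplaced. It is not: completely missing start dates are left alone, ordinary pre-dose occurrences are not in the AE data, and for events collected from dosing onward the rule does what it should. A reader might also infer that the rule attributes a pre-dose event to the drug. It does not: on-treatment is a timing class, while drug-relatedness comes from its own item and is tabulated separately.

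**Conclusion.** The rule is wrong as written for events whose recorded data already place the onset before dosing. It contradicts the Pre-Treatment phase in SAP 6.2.2.3, and nothing elsewhere in the SAP repairs it. Every event that fits the pattern is misclassified, but few, and quite possibly none, will occur.

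The 10-point effect is an upper figure. It assumes a cohort of 10 and no other on-treatment SAE in the same participant, because incidence is counted by subject. The any-SAE row, the drug-related rows, the partial dates shown in listings and the primary PK endpoint are unaffected. This is a minor correction to a derivation rule and does not put the study's conclusions in doubt.

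**What to change.** Add a condition to SAP 6.2.6 for starts whose imputed value falls before dosing:

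> Replace the imputed start with the dosing date and time only if (a) the recorded part of the start date is compatible with onset on or after dosing, meaning the dosing day with the time missing or the dosing month and year with the day missing, and (b) any recorded stop date is not before dosing. Otherwise keep the imputed start and class the event as Pre-Treatment under 6.2.2.3.

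The same sentence should confirm that the rule covers a fully dated event with only the clock time missing, which settles the ambiguity in the lead-in. The cost is one sentence in the SAP and one condition in the AE derivation program, with no change to data collection. The SAP leaves extra data-handling detail to the Output and Programming Specification, but the on-treatment consequence is stated in the SAP itself, so the correction belongs there.

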**Study period (26 weeks)**

Participants will be admitted the day before dosing, and all participants will remain in the clinical research unit (CRU) for approximately 8 hours after dosing for safety observation and other procedures. In the event of an acute severe reaction (e.g., anaphylaxis) following administration of study intervention, there are personnel/staff onsite at the treatment facility who are appropriately trained in basic life support to manage the participant including administration of medications (e.g., epinephrine), and have access to a system that can promptly transport the participant to another facility for additional care if appropriate. Participants will be discharged only if the Investigator deems it safe for the participant to leave the unit.

Participants will return to the CRU for regular out-patient visits throughout the study according to Schedule of Activities.

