The primary clinical question of interest is: The pharmacokinetic target estimand aims to assess the PK profile in Chinese healthy participants with two dose levels of GSK3511294 administered subcutaneously in the absence of prohibited medication potentially impacting GSK3511294 PK profile.

The estimand is described by the following attributes:

Population	Chinese healthy male and female participants aged 18 to 45 years
Treatment	100 mg or 300 mg GSK3511294
Intercurrent events (ICE)	If use of prohibited medication is considered to impact on GSK3511294 PK profile, it will be addressed with hypothetical strategy and in such case the individual PK concentrations after ICE would be treated as missing in Non-compartmental analysis (NCA). Otherwise, it will be addressed with treatment policy and the individual PK concentrations after the occurrence of ICE will still be included into PK analysis.
Endpoints	Plasma pharmacokinetic parameters: AUC(0- ∞), AUC(0-t), AUC(0-Week4), AUC(0-Week12), AUC(0-Week26), %AUCex, Cmax, tmax, tlast, CL/F, Vz/F, λ_z and t $\frac{1}{2}$
Summary Measure	Geometric mean: AUC(0- ∞), AUC(0-t), AUC(0-Week4), AUC(0-Week12), AUC(0-Week26), %AUCex, Cmax, CL/F, Vz/F, λ_z and t $\frac{1}{2}$ Median: tmax, tlast

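### Partial medication start dates are imputed with no floor at dosing, so drugs that may have started after dosing are tabulated as Pre-Treatment, and two SAP sections disagree on the cut-off

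*SAP*

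**What the plan says.** **Partial medication dates (SAP 6.2.6).** For a start date: "If the partial date is start date, a '01' will be used for the day and 'Jan' will be used for the month". For an end date: "If the partial date is a stop date, a '28/29/30/31' will be used for the day", with December if the month is missing. Listings show the date as recorded.

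**Medication phase (SAP 6.2.2.2).** The split is "Pre-Treatment: Start Date < Dosing Date", and On-Treatment otherwise. A note under the table sends the reader to 6.2.6 and adds: "Use the rules in this table if concomitant medication date is completely missing". Partial dates therefore take the 6.2.6 imputation and are then compared with dosing.

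**The same split in SAP 6.1.4.** There it reads "Pre-Treatment: Start Date and Time < Dosing Date and Time". This section also plans separate summaries of prior, pre-treatment and on-treatment medications.

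**Partial adverse event dates (SAP 6.2.6, same table).** A missing start day becomes the first of the month unless that precedes dosing; "in this case the study treatment start date and time will be used", and the event counts as On-Treatment.

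**The concern.** The medication rule always chooses the earliest date compatible with the record and never asks whether that date crosses dosing. A start known only to lie in the dosing month is pushed before dosing unless dosing was on the 1st. The adverse event rule resolves the same uncertainty the other way, and the SAP gives no reason for the difference. A reader who compares on-treatment events with on-treatment medications could find the event in one table and its treatment missing from the other.

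The two phase tables also disagree with each other, and that needs no partial date at all.

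Partial dates are plausible here. On Day 1 "all participants will remain in the clinical research unit (CRU) for approximately 8 hours after dosing"; after that they are outpatients, and from Day 85 to Day 169 visits are six weeks apart (Protocol 1.3). SAP 6.2.6 itself provides for partial dates.

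**Working it through.** The plan gives no figure on this point, so there is none to reproduce. The check applies the stated rules to examples and then counts. I read the start-date rule as filling in only the missing parts.

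**Worked examples, dosing on 15 June**

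| True start | Recorded | Imputed (6.2.6) | Phase (6.2.2.2) |
|---|---|---|---|
| Drug, 20 June (Day 6) | June | 1 June | Pre-Treatment |
| Adverse event, 20 June | June | 1 June, moved to 15 June | On-Treatment |
| Drug, 10 September (Day 88) | September | 1 September | On-Treatment |
| Drug, 10 September (Day 88) | year only | 1 January | Pre-Treatment |

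With only the day missing, the error is confined to starts in the dosing month. The end-date rule does not correct it, because the pre-/on-treatment split uses the start date alone.

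**Share of start days affected, day missing**

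Assumptions: dosing dates uniform over a 365-day year, and true start dates uniform from Day 1 to Day 183.

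- Dosing on day d of a month of length L leaves L − d + 1 start days in that month on or after dosing. All of them flip if d > 1, and none if d = 1.
- Summing over d = 2 to L gives L(L − 1)/2 per month: 465 for 31 days, 435 for 30 days, 378 for 28 days.
- Over the year: 7 × 465 + 4 × 435 + 378 = 5,373.
- All dosing-date and start-day pairs: 365 × 183 = 66,795.
- Share: 5,373 / 66,795 = 8.0%.
- Over Day 1 to Day 211: 5,373 / (365 × 211) = 5,373 / 77,015 = 7.0%.

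**Share affected, day and month missing**

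- A start flips if it falls in the dosing year, except when dosing is on 1 January.
- Dosing on days 2 to 183 of the year: 182 × 183 = 33,306 pairs.
- Dosing on days 184 to 365: 182 + 181 + … + 1 = 16,653 pairs.
- Share: (33,306 + 16,653) / 66,795 = 49,959 / 66,795 = 74.8%.

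These are shares of true post-dose start days among records with that kind of partial date. They are not shares of participants or of all medications.

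**With a floor at dosing**, as in the adverse event rule, both shares fall to 0%.

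**The two cut-offs.** Take a drug started on Day 1 some hours before dosing, with date and time complete. Under 6.1.4 its start precedes the dosing date and time, so it is Pre-Treatment. Under 6.2.2.2 its start date equals the dosing date, so it is On-Treatment.

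**The case against.** The defence has several good points.

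- Protocol 6.9 requires start and end dates for every medication, and participants must generally abstain from other drugs. Partial dates should be few.
- Visits fall on Days 2, 3, 5, 8, 15, 29, 57, 85, 127, 169 and 183, so gaps never exceed 42 days. A post-dose start known only by year is hard to credit, and the 74.8% should carry little weight.
- The adverse event rule covers a missing day only. It says nothing about year-only dates, so the contrast does not extend to them.
- Counting doubtful adverse events as on-treatment is a safety convention, and medications need not follow it.
- The record stays concomitant, and the listing shows the date as recorded.

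All of this limits the size. It does not remove the misclassification in the dosing month or reconcile the two cut-offs.

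A reader might go further and infer that the primary analysis is affected. Prohibited medication use is the only intercurrent event in the primary PK estimand, and when that use is considered to affect PK, SAP 1.1 says "individual PK concentrations after ICE would be treated as missing in Non-compartmental analysis (NCA". That step needs a date. If the imputed date were used, a pre-dose value could either hide the event or remove all of a participant's post-dose concentrations and cost precision. The documents do not support this as a description of the plan. SAP 1.1 does not tie the event's date to 6.2.6, and the handling turns on a judgement about PK impact. SAP 6.1.3 has deviations tracked and reviewed before the database is frozen, although it sets no event dates either. What stands is that the SAP does not say which date applies, and one sentence would settle it.

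**Conclusion.** The point holds as a defect in the medication phase rules. As written, they class a drug that may have started after dosing as Pre-Treatment, place an event and its treatment on opposite sides of dosing when both lack the start day, and give two answers for a Day 1 pre-dose drug.

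The certain effect is limited to the pre-/on-treatment medication summaries. With only the day missing, about 8% of start days over Day 1 to Day 183 are affected, assuming uniform dosing and start dates. The documents do not give the frequency of partial dates, so no count of participants can be stated; with about 10 per cohort and dates required in the eCRF, few are likely to be affected. No loss of participants or precision in the primary PK analysis can be claimed. This is a minor correction worth making.

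**What to change.** 1. In SAP 6.2.6, add for phase classification: when the recorded part of a medication start date is compatible with a start on or after dosing, and the stop date is not before dosing, class the medication as On-Treatment.
2. Use one identical cut-off in 6.1.4 and 6.2.2.2. Date and time separates Day 1 use before and after dosing and matches the adverse event phases in 6.2.2.3, but needs a line for a missing time. Date alone needs no such line, but counts Day 1 pre-dose use as On-Treatment.
3. State that this imputed date is not used to date a prohibited-medication intercurrent event, which is dated from the recorded date and documented case review. This must accompany item 1: a date floored at dosing would otherwise set all of that participant's post-dose concentrations to missing. Where the recorded date is itself partial, the review should document the date chosen and why.

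The cost is a few sentences in the SAP and a small programming change. The downside is that a few medications that truly started before dosing will be shown as on-treatment; the recorded dates in the listings will let a reader see which.
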